## 1.0 Objectives

### 1.1 Study Objectives

In this study, we will test the central hypothesis that postmenopausal women will demonstrate increased oxygen extraction in active leg muscle during leg cycling exercise while receiving an infusion of Esmolol, a fast-acting  $\beta_1$  selective antagonist, when compared to premenopausal women.  $\beta_1$  selective antagonists (or “ $\beta_1$  blockers”) are used to lower heart rate and improve  $O_2$  supply-to-demand balance in patients with coronary artery disease. By using esmolol to attenuate the central sympathetic response to exercise (increased heart rate and cardiac output) we can examine peripheral mechanisms of  $O_2$  delivery. The current project will evaluate how older postmenopausal women adjust active muscle  $O_2$  supply to an acute reduction in systemic  $O_2$  delivery during large muscle dynamic exercise when compared to younger premenopausal women.

### 1.2 Primary Study Endpoints

The primary outcome variable is the difference in the change in skeletal muscle oxygenation (% $\Delta SmO_2$ ) in the active leg muscle from baseline during recumbent cycling exercise between saline and esmolol ( $\Delta\% \Delta SmO_2$ ). We predict that older women will have a greater  $\Delta\% \Delta SmO_2$  than premenopausal women during esmolol infusion.

### 1.3 Secondary Study Endpoints

Secondary outcome variables will include the effect of concurrent sympathetic stimulation via isometric handgrip exercise on active thigh and inactive forearm muscle  $\Delta\% \Delta SmO_2$ . We will also include measurements of blood pressure, heart rate, cardiac output, and  $VO_2$ .

## 2.0 Background

### 2.1 Scientific Background and Gaps

Understanding the mechanisms facilitating the acute adjustments in oxygen uptake ( $VO_2$ ) during large muscle exercise is biomedically important, as it is a major determinant of exercise tolerance and functional quality of life in both health and disease. The physiological adjustments that mediate increases in  $VO_2$  during exercise are highly integrated and involve increases in mean arterial pressure (MAP), systemic and exercising muscle blood flow, and arterial-venous  $O_2$  content (primarily via increased  $O_2$  extraction). The matching of  $O_2$  delivery-to-utilization/demand during dynamic exercise, and the speed with which these processes occur at exercise onset (kinetics), reflects the integrated functioning of the autonomic, pulmonary, cardiovascular, and muscular metabolic systems which in turn determine the necessity for substrate-level (nonoxidative) energy supply and subsequent exercise tolerance/intolerance.

Interventions that alter the normal balance between sympathetic control, active muscle  $O_2$  supply, and extraction have the potential to advance our understanding of the mechanisms regulating kinetic and steady state  $VO_2$  responses to exercise. Studies employing beta-adrenergic blockade, which acutely reduce heart rate, contractility, and systemic  $O_2$  delivery (refs), report compensatory increases in systemic and leg arterial-venous  $O_2$  content difference during submaximal cycling exercise in healthy younger humans.

Age- and sex-related differences in  $O_2$  utilization. It has been previously shown that older women demonstrate an attenuated ability to increase cardiac output and leg vascular conductance during moderate-intensity (50-60 watts) cycling exercise resulting in reduced leg blood flow and  $O_2$  delivery. However, unlike older men (who displayed no reduction in leg blood flow during exercise), older women did not demonstrate an increase in  $O_2$  extraction compared to their younger counterparts. It is unclear whether these differences represent a better-preserved ability to deliver oxygen to active muscle or an impairment in oxygen extraction. By infusing esmolol during exercise, we will attempt to further reduce oxygen delivery to examine oxygen extraction in young vs older women.

Age-related reductions in Functional Sympatholysis. Previous studies, both from our lab and others, indicate substantial age differences in the ability of metabolically active muscles to blunt sympathetic vasoconstriction (functional sympatholysis). The age-related attenuation of this response is particularly evident in older post-menopausal women and could contribute, along with an accelerated stiffening of central arteries and altered baroreflex function, to the exaggerated systemic blood pressure responses observed in these women when they perform dynamic exercise. Isometric handgrip has been established as a reliable way to acutely augment systemic sympathetic outflow and NIRS has been used to assess the resultant functional sympatholysis response in various populations including in post-menopausal women. The present study will assess how functional sympatholysis is affected by an acute esmolol-mediated reduction in cardiac output during dynamic cycling exercise and how this response may differ between younger and older women.

## 2.2 Previous Data

Because of its rapid onset and offset, Esmolol is used commonly in anesthesia and critical care to treat tachycardia. Our dose-finding studies indicated that infusing of ~125 mg of Esmolol (range 90 to 162 mg) acutely blocks beta-1 adrenergic receptors ( $\beta$ 1ARs) in healthy young men and women.  $\beta$ 1ARs remain blocked in these subjects if a maintenance infusion of Esmolol continues. When the infusion ends, the  $\beta$ 1ARs return to baseline within 45 minutes.

There are minimal published data using Esmolol in the context of exercise physiology experiments. The [name] lab recently utilized the rapidly acting  $\beta$ 1 selective antagonist esmolol to transiently reduce exercise heart rate in a mixed (age and sex) sample of healthy adults. Larger reductions in near infrared spectroscopy (NIRS)-derived oxyhemoglobin/myoglobin O2 saturation (an index of O2 extraction) were observed within the exercising leg muscles (vastus lateralis and medial gastrocnemius) of these subjects during esmolol (vs. saline) infusion. These findings provide strong evidence of the dynamic coupling that exists between systemic O2 delivery and active muscle O2 extraction during submaximal exercise in humans.

## 2.3 Study Rationale

The effects of infused Esmolol on the heart are rapid (observed within 5 min), quickly reversible (9 min half-life), and do not provoke lightheadedness, nausea, or significant hypotension in healthy adults. This is in contrast to non-selective ( $\beta$ 1+ $\beta$ 2) blockers such as Propranolol, which are not rapidly reversible. The use of  $\beta$ 1-selective blockade is also advantageous in these studies because it does not impact  $\beta$ 2-mediated responses in skeletal muscle (as we have shown with Esmolol) and does not appear to suppress skeletal muscle glycolysis or hasten exercising muscle fatigue in the way that non-selective blockade does.

# 3.0 Inclusion and Exclusion Criteria

## 3.1 Inclusion Criteria

1. Capable of giving informed consent
2. Premenopausal women ages 18-35 years OR post-menopausal women ages 55-70 years
3. Satisfactory medical history and physical exam, as determined by a CRC clinician
4. Not currently taking medications affecting heart rate or contractility
5. Fluent in written and spoken English

## 3.2 Exclusion Criteria

Participants who will not be studied are those who:

1. Are less than 19 years of age or more than 70 years of age
2. Are pregnant or lactating
3. Are prisoners or institutionalized individuals or unable to consent

4. Diagnosed renal failure (Creatinine >2.0 mg/dl)
5. Diagnosed liver disease (ALT and AST 2 times normal)
6. Diagnosed Reynaud's disease
7. Have uncontrolled diabetes
8. Have uncontrolled hypertension
9. Have a left ventricular ejection fraction < 40%
10. Have a recent history of unstable angina or myocardial infarction (<6 months), unstable angina, or use of nitrate medications within past 2 weeks
10. Severe lung disease (i.e., on supplemental oxygen or frequently use rescue inhalers)
11. Diagnosed bleeding or clotting disorder or recent blood transfusion
12. Have asthma, history of thyroid issues or hyperkalemia
13. Known use of recreational drugs
14. Methylphenidate use

### **3.3 Early Withdrawal of Subjects**

#### **3.3.1 Criteria for removal from study**

Participation in this study will be discontinued if pre-screening requirements are not met, pregnancy, failure to follow pre-study instructions or main variables cannot be measured. If vital signs fall below or rise above acceptable levels or if the subject does not tolerate a procedure, the procedure will be stopped. The subject may withdraw from the study at any time.

#### **3.3.2 Follow-up for withdrawn subjects**

Subjects withdrawn from the study will not return for any more visits. The research nurses will contact subjects after withdrawal to ensure there are no further problems.

## **4.0 Recruitment Methods**

### **4.1 Identification of subjects**

Subjects will be identified from our own subject pool who meet the inclusion/exclusion criteria and previously agreed to be contacted.

Subjects will also be recruited from Penn State campus, State College community, and Centre County area by flyers and advertisements. Flyers will contain basic information about the study, as well as contact information for study personnel in the Integrative Vascular Physiology Laboratory (201 Noll Lab). Potential participants who show interest in the study by contacting study personnel will be sent an informed consent form over email with instructions to contact one of the study investigators if she has any questions or would like to schedule a visit to Noll Lab for the screening and familiarization visit.

In addition to flyers and advertisements, StudyFinder will be used for recruitment purposes.

### **4.2 Recruitment process**

#### **4.2.1 How potential subjects will be recruited.**

Subjects will be recruited through the CRC and through study finder. Potential subjects, who are interested in participating, will be informed about the details of the study using the phone script. If they are interested in participating, then they will be informed that a series of pre-screening questions pertaining to their health, medical background and history (Patient Information sheet) will be asked over the phone and that by answering the questions, they will be giving their consent to allow us to use and retain that information. If subjects wish to participate in additional research

studies, they may indicate that they allow their information to be retained and used in the future by the research group to contact them about future studies. If they indicate that they are not interested in future studies, their information will be destroyed at the end of this study or at any future time when they request destruction. The information will not be disclosed to anyone outside of the CRC Research team

No race or ethnicity will be excluded from the study.

#### **Recruitment materials**

Invitation to participate/Permission to contact letter  
Phone screening questions  
StudyFinder  
Study Flyers

#### **4.2.2 Where potential subjects will be recruited.**

Subjects will be identified from our own subject pool who meet the inclusion/exclusion criteria and previously agreed to be contacted.

Potential subjects will be recruited from State College, PA and the surrounding region (i.e., Centre County).

#### **4.2.3 When potential subjects will be recruited.**

Recruitment of potential subjects will begin upon study approval.

#### **4.2.4 Describe the eligibility screening process and indicate whether the screening process will occur before or after obtaining informed consent. Screening begins when the investigator obtains information about or from a prospective participant in order to determine their eligibility. In some studies, these procedures may not take place unless HIPAA Authorization is obtained OR a waiver of HIPAA Authorization when applicable for the screening procedures is approved by the IRB.**

Members of the Integrative Vascular Physiology Laboratory will answer phone calls (office phone) or emails from potential participants. During these exchanges, prospective participants may ask any questions regarding the study and/or schedule a visit to complete informed consent and screening process.

After signing the IRB approved consent the subjects will participate in the screening visit a brief medical history, physical exam, resting EKG, and blood draw (CBC and CMP) will be performed to confirm each participant's health status. Women of childbearing potential will have a urine pregnancy test to confirm they are not pregnant. We will also have subjects fill out a physical activity history questionnaire. These questionnaires will not be used to determine study eligibility (inclusion or exclusion), but will be used to describe the study groups in future publications.

## **5.0 Consent Process and Documentation**

### **5.1 Consent Process:**

**Check all applicable boxes below:**

**Informed consent will be sought and documented with a written consent form**

- Implied or verbal consent will be obtained – subjects will not sign a consent form (waiver of written documentation of consent)**
- Informed consent will be sought but some of the elements of informed consent will be omitted or altered (e.g., deception).**
- Informed consent will not be obtained – request to completely waive the informed consent requirement.**

## 5.2 Obtaining Informed Consent

### 5.2.1 Timing and Location of Consent

Prior to coming to the laboratory, subjects will be contacted using the Study Prep phone script. The participants will avoid alcohol and strenuous exercise for 24 hours prior to each study visit. Participants will also refrain from caffeine at least 12-24 hours and NSAIDS/cold prep medications 24 hours prior to each study visit. Participants will be asked to eat a small meal 2 to 3 hours before their scheduled appointment but dietary intake will not be rigorously controlled. ALL participants will review their prescribed medications, with a CRC (Clinical Research Center) clinician.

Once the subject arrives at the CRC, they will be given sufficient time to read the consent, all procedures will be explained in layman's terms and they will be given a copy of the signed consent form.

### 5.2.2 Coercion or Undue Influence during Consent

The subject will be provided with ample opportunity to have questions answered before participating in the study. All procedures will be explained to them in layman's terms and they will be given a copy of their signed consent form. Subjects will have the right to withdraw from the study at any time.

## 5.3 Waiver of Written Documentation of Consent

N/A Subjects will sign the IRB-approved consent form.

### 5.3.1 Indicate which of the following conditions applies to this research:

- The research presents no more than minimal risk of harm to subjects and involves no procedures for which written consent is normally required outside of the research context.  
OR
- The only record linking the subject and the research would be the consent document and the principal risk would be potential harm resulting from a breach of confidentiality. Each subject will be asked whether the subject wants documentation linking the subject with the research, and the subject's wishes will govern.  
OR
- If the subjects or legally authorized representatives are members of a distinct cultural group or community in which signing forms is not the norm, that the research presents no more than minimal risk of harm to subjects and provided there is an appropriate alternative mechanism for documenting that informed consent was obtained.

**5.3.2 Indicate what materials, if any, will be used to inform potential subjects about the research (e.g., a letter accompanying a questionnaire, verbal script, implied consent form, or summary explanation of the research)**

Subjects will be contacted using the Study Prep phone script to obtain verbal consent to avoid alcohol and strenuous exercise for 24 hours prior to the experiments. This poses no more than minimal risk, so verbal consent is appropriate. Once the subject arrives in the Clinical Research Center (CRC), they will be given sufficient time to read the consent form and have all their questions answered, and to sign the written consent.

**5.4 Informed consent will be sought but some of the elements of informed consent will be omitted or altered (e.g., deception).**

**5.4.1 Indicate the elements of informed consent to be omitted or altered. - Not applicable**

**5.4.2 Indicate why the research could not practicably be carried out without the omission or alteration of consent elements. - Not applicable**

**5.4.3 Describe why the research involves no more than minimal risk to subjects. Not applicable**

**5.4.4 Describe why the alteration/omission will not adversely affect the rights and welfare of subjects. Not applicable**

**5.4.5 If the research involves using identifiable private information or identifiable biospecimens, describe why the research could not be practicably be carried out without using such information or biospecimens in an identifiable format. Not applicable**

**5.4.6 Debriefing Not applicable**

**5.5 Informed consent will not be obtained – request to completely waive the informed consent requirement**

**5.5.1 Indicate why the research could not practicably be carried out without the waiver of consent- Not applicable**

**5.5.2 Describe why the research involves no more than minimal risk to subjects.**  
Not applicable

**5.5.3 Describe why the alteration/omission will not adversely affect the rights and welfare of subjects**  
Not Applicable

**5.5.4 If the research involves using identifiable private information or identifiable biospecimens, describe why the research could not be practicably be carried out without using such information or biospecimens in an identifiable format.**  
Not applicable

**5.5.5 Additional pertinent information after participation. - Not applicable**

**5.6 Consent – Other Considerations**

**5.6.1 Non-English-Speaking Subjects - Not applicable**

**5.6.2 Cognitively Impaired Adults.**

**5.6.2.1 Capability of Providing Consent - Not applicable**

**5.6.2.2 Adults Unable to Consent - Not applicable**

**5.6.2.3 Assent of Adults Unable to Consent - Not applicable**

**5.6.3 Subjects who are not yet adults (infants, children, teenagers)**

**5.6.3.1 Parental Permission - Not applicable**

**5.6.3.2 Assent of subjects who are not yet adults - Not applicable**

**6.0 HIPAA Research Authorization and/or Waiver or Alteration of Authorization**

**6.1 Authorization and/or Waiver or Alteration of Authorization for the Uses and Disclosures of PHI**

**Check all that apply:**

- Not applicable, no identifiable protected health information (PHI) is accessed, used or disclosed in this study.
- Authorization will be obtained and documented as part of the consent process.
- Partial waiver is requested for recruitment purposes only (Check this box if patients' medical records will be accessed to determine eligibility before consent/authorization has been obtained).
- Full waiver is requested for entire research study (e.g., medical record review studies).
- Alteration is requested to waive requirement for written documentation of authorization (verbal authorization will be obtained).

**6.2 Waiver or Alteration of Authorization for the Uses and Disclosures of PHI**

**6.2.1 Access, use or disclosure of PHI representing no more than a minimal risk to the privacy of the individual**

**6.2.1.1 Plan to protect PHI from improper use or disclosure**

Not applicable

**6.2.1.2 Plan to destroy identifiers or a justification for retaining identifiers**

Not applicable

**6.2.2 Explanation for why the research could not practicably be conducted without access to and use of PHI**

Not applicable

### **6.2.3 Explanation for why the research could not practicably be conducted without the waiver or alteration of authorization**

Not applicable

### 6.3 Waiver or alteration of authorization statements of agreement

Protected health information obtained as part of this research will not be reused or disclosed to any other person or entity, except as required by law, for authorized oversight of the research study, or for other permitted uses and disclosures according to federal regulations.

The research team will collect only information essential to the study and in accord with the 'Minimum Necessary' standard (information reasonably necessary to accomplish the objectives of the research) per federal regulations.

Access to the information will be limited, to the greatest extent possible, within the research team. All disclosures or releases of identifiable information granted under this waiver will be accounted for and documented.

## 7.0 Study Design and Procedures

## 7.1 Study Design

**Design:** single blind, randomized, placebo-controlled, crossover (each person receives both treatments)

**Subjects:** young and older women (2 groups, n=13 completed subjects each)

**Independent variable:**  $\beta_1$  selective blockade with Esmolol vs. saline

[figure not shown]
**Dependent variables:** heart rate, cardiac output, arm BP, finger BP,  $\text{VO}_2$ , forearm, forehead, thigh and calf NIRS

**There will be one screening visit and two study visits (one non-infusion and one infusion).** The procedures for each visit are outlined in the diagram below:

[figure not shown]
## Visit 1: Screening visit

## Visit 2: Non-infusion

## Visit 3: Infusion

This is a single-blind study because, although the subjects, data collectors, and data analysts will not be aware of the treatment order, the nurses monitoring the subjects will be aware of the label on the infusion bag (Esmolol or saline). The nurses will be assessing safety (i.e., HR, BP, and symptoms). However, the nurses will not be involved in any data analysis.

Esmolol hydrochloride (2500 mg in 250 ml normal saline) will be purchased from McKesson in pre-mixed bags. The placebo will be a 250 ml, 500 ml, or 1000 ml bag of normal saline. The volume and rate of infusion will be constant for both trials. Once the infusion pump is programmed by the research nurse, an opaque bag will be placed over the fluid bag so that the participants and researchers remain blinded to the treatment order.

[figure not shown]
## 7.2 Study Procedures

### 7.2.1 Visit 1 (screening visit)

When research staff schedules the subject (over the phone), the subject will be told to avoid alcohol, over-the-counter cold prep and NSAIDs, and strenuous exercise for 24 hours, and to eat a small meal 2-3 hours prior to coming to the laboratory. They will also be asked to refrain from items containing caffeine 12 hours prior to this visit. All participants will review their medications, including beta-blockers, with one of the research nurses. This information will be shared with the CRC clinician who will then recommend which medications can be taken prior to the patient's scheduled second and third study visit, and which ones should be withheld until after each study visit.

During the first visit, informed consent will be obtained. Women of childbearing potential (pre-menopausal) will take a urine pregnancy test to ensure they are not pregnant. This will be done at all 3 visits before conducting any of the study measurements. The subject will then complete a medical history questionnaire (all subjects) and a physical activity history questionnaire. The subject will also have their height and weight (without shoes) and waist circumference measured. The subject will then undergo a physical exam and a resting EKG (conducted by medical personnel). A venous blood draw will then be performed by a CRC nurse and sent for analysis (CBC and CMP; 7.5 ml total). Lab values will be verified/signed off by a CRC clinician before infusion begins, and will be obtained no more than 6 weeks prior to the infusion. During this first study visit, all subjects will also be asked to squeeze a handgrip device as hard as they can 3 times, with approximately 1 min recovery between each. After a short recovery, the subject will then be asked to squeeze the handgrip device for approximately 1 minute at 40% of their maximum effort. Immediately after, we will ask the subject how they tolerated the 40% grip task (rating of perceived effort scale). This procedure will familiarize the subject with the handgrip before they are asked to perform these tasks (for longer durations) during visits 2 and 3. Analysis of the blood

tests, EKG and medical history/exam results, and the subject's tolerance to the handgrip will collectively determine the final eligibility of the participant.

(Figure from Iannetta et al., 2020)

Then the subject will then lay on an exam bed for placement of EKG pads and a doppler ultrasound device will be used to determine skinfold thickness of the thigh. The NIRS sensors will then be placed (one on the forearm, one on the forehead and two on the leg). The subject will then be assisted onto the recumbent bike. The subject will be asked to squeeze a handgrip device as hard as they can with their hand. The maximum force they can exert (highest of 2 to 3 efforts) will be used to determine how hard they will squeeze this device later in the study (40% of this maximum value). A silicone face mask will be placed over the subject's nose and mouth to monitor their oxygen consumption and breathing frequency, and blood pressure devices will be placed over their arm (SunTech Tango) and finger (Finometer). After all instrumentation is in place, baseline measurements of heart rate, cardiac output, oxygen consumption, blood pressure, and NIRS will begin.

The subject will then be asked to complete three exercise bouts on a recumbent bike. The first bout will consist of very light pedaling for 2 minutes (warm-up) followed by approximately 6 minutes of pedaling at what should be a moderate effort for the subject. After a few minutes of rest and/or light pedaling (recovery), the subject will be asked to perform a second bout of exercise, which will consist of a very gradual increase in workload ("ramp") until the subject can no longer maintain the required pedal speed or needs to stop due to fatigue. This second bout will likely last between 6 and 12 minutes. After a few minutes of light pedaling, the face mask will be removed and the subject will recover in a comfortable chair. After 30 minutes of recovery, the subject will be assisted back on the bike and the facemask will be reattached. The subject will then pedal for 2 minutes at a very light workload, followed immediately by up to 12 minutes of pedaling at a moderately heavy workload. After a brief cool-down of light pedaling, the facemask and other sensors (e.g., EKG, NIRS, etc) will be removed. At several points throughout this visit (minimum of 3, maximum of 6) a small drop of blood from your fingertip will be used to measure the subject's blood lactate level. The measurements obtained during this first study visit will determine the exercise workloads that will be individually assigned during study visits 2 and 3.

Women who are currently taking hormone therapy of any kind (oral contraceptives, estrogen replacement, etc) will not be excluded from participation in this study. However, given the well-documented effects of female sex hormones on resting blood pressure and exercise metabolic responses we will ask 1) pre-menopausal women to indicate their current menstrual status and oral contraceptive use and 2) post-menopausal women to self-report their history and duration of sex hormone replacement. This information will be collected at the time of their medical history/physical exam.

[figure not shown]
Eligible participants will be asked to return for two experimental visits (non-infusion and infusion) at least 48 hours apart.

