#### **7.4.5 Prior and Concomitant Therapy**

A list of prior and current medications will be obtained during the screening visit as part of the medical history. Subjects will be asked to withhold all over-the-counter medications (e.g. motrin, cold medicine) for 24 hours prior to each study and during the study procedures. ALL participants will review their prescribed medications, including beta-blockers, with one of the research nurses. This information will be shared with the CRC clinician who will then recommend which medications can be taken prior to the patient's scheduled study visit, and which ones should be withheld until after the study. All medications consumed by the participants will be written on the flow sheet.

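### Do the medication-review sections let women on beta-blockers into a study that bars drugs affecting heart rate?

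*Combined protocol and SAP*

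**What the plan says.** Section 3.1, criterion 4, admits women who are "Not currently taking medications affecting heart rate or contractility". It gives no look-back period. Criterion 3 of the same section requires a medical history that a CRC clinician finds satisfactory.

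Section 7.2.1, on the screening visit, says: "All participants will review their medications, including beta-blockers, with one of the research nurses". The information goes to the CRC clinician, who advises which drugs may be taken before the second and third visits and "which ones should be withheld until after each study visit". Later in 7.2.1, final eligibility is said to rest on the blood tests, EKG, medical history and exam, and tolerance of the handgrip. The section ends by inviting eligible participants back for the two experimental visits.

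Section 7.4.5 repeats the review: "ALL participants will review their prescribed medications, including beta-blockers, with one of the research nurses". Its holding advice reads "which ones should be withheld until after the study". It places the list of prior and current medications within the screening medical history, and adds: "All medications consumed by the participants will be written on the flow sheet".

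Two other sections bear on the point. Section 3.3.1 says: "Participation in this study will be discontinued if pre-screening requirements are not met". Section 5.2.1 describes a similar review without mentioning beta-blockers: "ALL participants will review their prescribed medications, with a CRC (Clinical Research Center) clinician".

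**The concern.** Beta-blockers are the plainest example of what criterion 4 bars, and they are the one prescription class that the reviews in 7.2.1 and 7.4.5 name. Yet neither section says that finding one excludes a woman, and neither refers back to criterion 4. The only stated outcome is to take or to hold. Because 'currently' is undefined, staff working from 7.2.1 alone might treat a held drug as satisfying the criterion. The exclusion list in 3.2 sets a two-week window for nitrates, so the lack of one here stands out. Section 3.2 excludes only uncontrolled hypertension, so women with treated hypertension may well reach the review.

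The stake would be the primary outcome. Each woman's ΔΔSmO2 compares her esmolol trial with her saline trial. A woman still partly blocked from her own medication would not give an unblocked saline control, and her difference would shrink. In the older group that would pull the age contrast towards zero; in the young group it would inflate it. With 13 completers per group, one woman carries noticeable weight. Section 8.3 defines no analysis set that would deal with her.

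**Working it through.** **Order of events.** Take a woman prescribed a beta-blocker through the protocol as written.

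1. Her drug is recorded at screening as part of the medical history (7.4.5) and reviewed with a nurse, who passes it to the CRC clinician (7.2.1, 7.4.5).
2. The clinician must find the history satisfactory (3.1, criterion 3), and the history is among the items that fix final eligibility at visit 1 (7.2.1).
3. The holding advice in 7.2.1 concerns visits 2 and 3. When eligibility is decided, no hold for those visits has started. In the ordinary sense she is taking the drug, so she fails criterion 4.
4. Participation ends when pre-screening requirements are not met (3.3.1), and only eligible women are invited back (7.2.1).

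The take-or-hold advice therefore applies to the other medications of women who have already passed criterion 4. Naming beta-blockers in the review serves to find the women whom the criterion bars.

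**The two wordings of the hold.** Section 7.2.1 has "which ones should be withheld until after each study visit" and 7.4.5 has "which ones should be withheld until after the study". Section 7.4.5 uses 'study' for a single visit elsewhere: it asks for over-the-counter drugs to be stopped 24 hours before each study, and the sentence with the hold refers to the scheduled study visit. The wordings fit the same hold. The silence of 5.2.1 on beta-blockers contradicts neither.

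**The plan's sample size.** Inputs from 8.2: difference 5.8 (22.0 − 16.2), SD 4.78, two-sided 0.05, 80% power. Normal approximation: n = 2 × (1.960 + 0.842)² × 4.78² / 5.8² = 10.66, so 11 per group, as stated (power 81.2%). With the t distribution, power is 77.2% at 11 and 84.3% at the planned 13, where the noncentrality is 5.8 / (4.78 × √(2/13)) = 3.09 on 24 degrees of freedom.

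**What one affected woman would do.** The number of affected women (one) and the share f of her response that is lost are both assumptions; the documents give neither. One older woman shifts the difference by 22.0 × f / 13; one young woman shifts it by 16.2 × f / 13 the other way. Power is from simulation of the two-sample t test with 13 per group.

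| Case | Difference | Power |
|---|---|---|
| None affected | 5.80 | 84% |
| One older, f = 0.10 | 5.63 | 82% |
| One older, f = 0.25 | 5.38 | 77% |
| One older, f = 0.50 | 4.95 | 65% |
| One older, f = 0.75 | 4.53 | 48% |
| One older, f = 1 | 4.11 | 30% |
| One young, f = 0.50 | 6.42 | 89% |
| One young, f = 1 | 7.05 | 89% |
| One older left out (12 vs 13) | 5.80 | 83% |

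Power falls faster than the mean difference because an outlying value also enlarges the SD. The table shows sensitivity to an assumption; it does not estimate a loss under this plan. The f = 1 row needs a woman whose response disappears altogether although her drug was held, and the base value of 22.0 comes from three people.

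**The case for a change.** The strongest reply is that this reading has to be pieced together from Sections 3.1, 3.3.1, 7.2.1 and 7.4.5, while staff at screening work from a paragraph that offers holding as an outcome. A woman told to hold her drug could be recorded as not currently taking it, and no sentence forbids that. At this sample size one contaminated value costs far more than one lost participant (65% power at half loss, against 83% with her left out), and the ceiling of 20 enrolled per group leaves room to replace her. A clarification would cost almost nothing.

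Part of this stands. 'Currently' is undefined, and a woman who stopped a heart-rate drug shortly before screening, or started one after it, is not expressly covered. A cross-reference to criterion 4 would make 7.2.1 and 7.4.5 easier to follow. But no passage says that a beta-blocker user may enrol, so there is an ambiguity here and no contradiction. The damaging case needs staff to overlook criterion 4, a user to come forward, and substantial block to outlast the hold.

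A line in 8.3 limiting the primary set to women who met criterion 4 at visit 3 would not help. It relies on the same undefined term, and it would fix the timing of an eligibility rule that belongs to the clinical team. The absence of a defined analysis set in 8.3 is a separate, general matter.

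**Conclusion.** The concern does not call for a change. Followed as written, the protocol excludes current users of heart-rate drugs at visit 1, before the holding advice for visits 2 and 3 comes into play. What is left is missing detail that the CRC clinician, who judges the medical history and receives the medication review, can settle case by case. The flow-sheet record of medications in 7.4.5 lets the analyst identify any exception.

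No effect on power can be derived from the documents. The range of 82% to 30% for one affected older woman depends wholly on assumed use and assumed residual block, and on a pilot mean from three people. The conclusion assumes that criterion 4 is applied at screening in its ordinary sense. It takes no position on how long a drug must have been stopped, which is for the clinical team.
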